4.2 Key Secondary Objective(s) & Endpoint(s)

Secondary objectives

- To evaluate the efficacy of TOFA with SLE-CL over time compared to baseline

Secondary endpoint

Part A and B:

- Proportion of subjects that achieve a skin response (complete or partial response) as per the validated (CLASI) at weeks 4, 8 and 24 compared to baseline at TD1¹⁴. Response is defined as follows:
 - *Complete response (CR)* : complete resolution of the inflammatory rash (CLASI activity score = 0);
 - *Partial response (PR)*: $\geq 20\%$ improvement of the CLASI activity score. A partial response (PR) is considered clinically significant
 - *No response*: $< 20\%$ improvement or even worsening of the CLASI activity score
 - *Cutaneous relapse*: a new CLASI activity score ≥ 4 in those subjects who previously achieved CR of SLE-CL (CLASI=0)

4.3 Exploratory Objective(s) & Endpoint(s)

Exploratory objectives

Part A:

- To evaluate single cell expression patterns of skin biopsies of affected and non-affected skin with TOFA therapy
- To examine changes in interferon α/γ receptor, STAT phosphorylation patterns with TOFA therapy using immunohistochemistry
- To investigate mRNA expression patterns in peripheral blood upon treatment with TOFA with focus on interferon regulated genes

Parts B and C:

- To evaluate steroid sparing properties of TOFA for SLE-CL
- To evaluate TOFA effect of overall disease activity in SLE as measured by the SLEDAI and BILAG
- To evaluate effects of TOFA on quality of life as measured by the Skindex (appendix 4) and overall well-being

Exploratory endpoints at week 4, 8, 12, 24, 52, and 76

Part A: Pharmacodynamics (PD)

- PD parameters include assessment of inhibitory effect of TOFA on expression of IL-2 responsive target genes downstream of the JAK/STAT pathway, such as FOXP3, SOCS3, IL-2R α , interferon - γ and granzyme B.

Parts B and C:

- Decrease of absolute dose of systemic CS from baseline
- Decrease of body weight adjusted CS dose from baseline
 - CS dosing is measured in prednisone-equivalents
- Proportion of subjects who discontinue systemic CS
- Proportion of subjects with cutaneous relapse
- Change of BILAG score from baseline¹³
- Absolute value and percent change in plasma: Complement C3 and C4d, autoantibodies (anti-dsDNA)
- Change in number of inflamed joints from baseline¹⁴
- Change in SKINDEX score from baseline¹⁵
- Change of CLASI damage score¹⁶ from baseline
- Change in SLEDAI score at each time point
- Change in protein: creatinine ratio at each time point.
- Change in subject's overall well-being at each time point
- Change in subject's ESR
- Proportion of subjects with clinically important reduction in SLE activity at each time point, based on CRV changes compared to baseline
- Proportion of subjects with flare of SLE activity at each time point, as defined by the BILAG¹⁷

Data of subjects who enter Part B before week 8 and/or Part C before week 24 will be considered on a last-observation (LOC) carried forward basis for endpoints of Part A and B, respectively.

5. Study Participants

5.1 Inclusion Criteria

1. Male or female ≥ 18 years of age and ≤ 45 years of age and > 40 kg body weight.
2. Fulfilled at least 4 out of the 11 Classification Criteria for SLE by the time of screening¹⁸.
3. Willing to give written informed consent, must fully understand the requirements of the trial, and must be willing to comply with all trial visits and assessments.
4. CLASI activity score of 8 or higher¹⁹ at screening and baseline despite standard of care therapy.
5. Stable dose of prednisone of ≤ 20 mg/day within 2 weeks of enrollment.

6. Female subjects of childbearing potential must use a highly effective method of contraception to prevent pregnancy (abstinence is considered highly effective) and must agree to continue to practice adequate contraception for the duration of their participation in the trial and for 28 days after their last dose of TOFA.
7. Female subjects of childbearing potential must have a negative serum pregnancy test at screening and a negative urine pregnancy test at Trial Day 1 before dosing.
8. For subjects receiving leflunomide treatment, total daily dose does not exceed 20 mg.
9. A negative QuantiFERON-TB Gold In-Tube test performed within the 3 months prior to screening, or within the screening period prior to baseline. A negative PPD test can be substituted for the QuantiFERON-TB.
10. Subjects either have protective varicella titers or evidence of having been vaccinated against varicella.

5.2 Exclusion Criteria

Subjects are not eligible for this trial if they fulfil any of the following exclusion criteria:

1. Mild SLE-CL defined as a CLASI activity score of 7 or lower at screening and baseline.
2. Increase in CS dosing within 2 weeks prior to Trial Day 1, or expected to require an increase in CS dosing during the first 4 weeks of the study.
3. Use of i.v. corticosteroids within 4 weeks prior to Trial Day 1.
4. Increase in dosing of methotrexate, leflunomide, within 4 weeks before Trial Day 1 or expected to require an increase during the first 8-weeks of the study.
5. Increase in dosing of hydroxychloroquine, or chloroquine within 4 weeks before Trial Day 1 or expected to require an increase during the first 8-weeks of the study.
6. Rituximab within 1 year of Trial Day 1.
7. Increase in dosing of any medication or herbal treatment considered to have immunosuppressive properties with 4 weeks before Trial Day 1.
8. Prior treatment with or known intolerance of TOFA.
9. Use of cyclophosphamide (i.v. or oral), cyclosporine, or tacrolimus within 12 weeks prior to Trial Day 1.
10. Treatment with other investigational agents within the last 6 months or 5 half-lives, or as per washout requirement from the previous protocol, whichever is longer.
11. Estimated glomerular filtration rate less than or equal to 60 mL/min /1.73 m².
12. Known positive Human Immunodeficiency Virus (HIV), Hepatitis C Virus (HCV), or Hepatitis B surface antigen (HBsAg) serology.

13. Any condition, including findings in the laboratory tests, medical history, or other screening assessments, that, in the opinion of the Investigator, constitutes an inappropriate risk or a contraindication for participation in the trial or that could interfere with the trial's objectives, conduct, or evaluation.
14. Active central nervous system SLE deemed to be severe or progressive and/or associated with significant cognitive impairment leading to inability to provide informed consent and/or comply with the protocol.
15. Significant renal disease due to a reason(s) other than Lupus Nephritis (e.g. diabetes mellitus, renovascular disease, or antiphospholipid syndrome).
16. Severely active Lupus Nephritis defined as a renal BILAG A score.
17. History of dialysis within 3 months prior to Trial Day 1 or expected to need during the trial.
18. History of or planned renal or other organ transplantation.
19. Known active clinically significant viral, bacterial or fungal infection, or any major episode of infection requiring hospitalization or treatment with parenteral anti-infectives within 8 weeks of screening, or completion of oral anti-infectives within 2 weeks of Trial Day 1.
20. Breastfeeding or currently pregnant.
21. Legal incapacity or limited legal capacity to provide informed consent or assent.
22. Blood dyscrasias, including:
 - Hgb <10 g/dL or Hct <33%.
 - WBC <3.0 x 10⁹/L.
 - Neutrophil count <1.2 x 10⁹/L.
 - Platelet count <100 x 10⁹/L.
 - Lymphocyte count of <0.5 x 10⁹/L.
23. AST or ALT > 1.5 times the upper limit of normal or any other clinically significant laboratory abnormality.
24. History of any other rheumatic autoimmune disease.
25. Infections:
 - Latent or active TB or any history of previous TB.
 - Chronic infections.
 - Any infection requiring hospitalization, parenteral antimicrobial therapy or judged to be opportunistic by the investigator within the 6 months prior to the first dose of study drug.
 - Any treated infections within 2 weeks.

- History of recurrent (more than one episode) herpes zoster or disseminated (a single episode) herpes zoster or disseminated (a single episode) herpes simplex.
- History or current symptoms suggestive of any lymphoproliferative disorder, including Cytomegaly Virus (CMV) or Epstein Barr Virus (EBV) related lymphoproliferative disorder, history of lymphoma, leukemia, or signs and symptoms suggestive of current lymphatic disease.

26. Subjects taking potent and moderate cytochrome P450 3A4 (CYP3A4) inhibitors (see Appendix 2).

27. Subjects taking potent and moderate CYP3A4 inducers (see Appendix 2).

28. Subjects who have been vaccinated with live or attenuated vaccines within the 6 weeks prior to the first dose of study medication. All subjects should be up-to-date with respect to standard of care vaccinations (as defined by their country health ministry) as permitted by past immunosuppressive therapy for SLE.

29. Subjects with a malignancy or with a history of malignancy with the exception of adequately treated or excised non-metastatic basal cell or squamous cell cancer of the skin or cervical carcinoma in situ.

30. Subjects with a history or current diagnosis of diverticulitis.

6 Treatments, Regimens & Control

This is a 3-part study designed to evaluate the Pharmacokinetics and Pharmacodynamics of TOFA in young adults with active SLE-CL (CLASI activity score>8) aged 18 to 45 years. Safety and efficacy will be evaluated as secondary objectives. Subjects achieving CR of SLE-CL may be permitted to roll-over to subsequent parts of the study earlier.

In Part A (baseline – week 8), subjects will be enrolled in an open-label arm to receive TOFA orally twice per day. PK analysis will be performed on Cohort 1 only to measure PK parameters. Starting week 4, subjects may roll over from Part A to Part B early, if there is clinical remission of SLE-CL (CLASI activity score = 0).

In Part B (week 8 – 24), subjects will continue TOFA as in Part A but CS can be decreased for clinically significant improvement of SLE-CL by $\geq 50\%$ from baseline. Subjects who maintain clinical remission of SLE-CL and succeeded in discontinuing CS, can roll over to Part C prior to week 24.

In Part C (week 24 – 76), subjects off CS who are in clinical remission of SLE-CL will be able to taper and change other background medications. TOFA dosage will remain stable.

It is planned to enroll:

Cohorts 1: n=10, weight > 40 kg age ≥ 18 up to and including 45 years.

Cohort 2: n=10; weight > 40 kg and age \geq 18 years up to and including 45 years. Enrollment of subjects into Cohort 2 will commence once enrollment of Cohort 1 are completed.

6.1 Treatment

1. **Active drug:** TOFACITINIB (TOFA)
2. **Allowable background anti-inflammatory systemic SLE therapy includes:**
 - a) Subjects on a stable dose of hydroxychloroquine for at least 1 month prior to study entry are permitted to continue use throughout the duration of the study with a maximum allowable dose of 400mg.
 - b) Subjects are permitted to continue the use of oral corticosteroids (CS), methotrexate (MTX), and leflunomide, at allowed doses, as well as NSAIDs and ASA.

6.2 Dosing

TOFA dosing: Twice daily orally

As documented in the TOFA Investigator brochure (Section 6.1; Version March 2016) doses up to 30 mg twice daily were safe and tolerated. However, for the purpose of this study only the dose of TOFA approved for rheumatoid arthritis (5 mg PO BID) will be tested.

Based on TOFA PK in the Rheumatoid Arthritis (RA) population [body weight (BW) ranging from 40 kg - 140 kg)], clearance (CL) of TOFA is not dependent on body weight in adult subjects. Thus, the starting dose of TOFA will be 5 mg orally twice daily, an approved dose of TOFA in adult RA subjects in most countries. Dose escalation will not occur even with lack of SLE-CL improvement.

Corticosteroids (CS):

At study entry, CS dosage must be \leq 20mg/day. CS should be kept stable up to and including week 4.

CS can be decreased starting week 5:

- CS may be decreased for improvement of the CLASI activity score by \geq 50% from baseline and must be tapered for CLASI activity scores of 0 for $>$ 8 weeks (or 2 subsequent study visits, whatever is shorter), provided CS are mainly prescribed for SLE-CL. This will minimize morbidity associated with CS use as much as possible.
- If CS are mainly prescribed for other SLE manifestations besides SLE-CL, then CS can be decreased as per the investigator's decision, even in the setting of complete response of SLE-CL, based on continued improvement of clinical findings of SLE.

Oral CS may be increased above the baseline level up to max of 60 mg/day for new BILAG A or B flares in organ systems other than mucocutaneous organ system (i.e. neurologic, ophthalmologic, musculoskeletal, cardiopulmonary, gastrointestinal, renal, hematological organ systems) but must be returned to baseline dose or lower within 14 days. If this is not achieved then the subject is considered a treatment failure.

- Up to 3 doses of pulse methylprednisolone may be given for new BILAG A or B flares instead.
- CS increases can occur no more than 3 times during the duration of the study, Part A- C.
- Subjects requiring more than 3 CS increases will be withdrawn from treatment phase of study.

Other anti-inflammatory medications used as part of standard of care (SOC) for SLE

These include methotrexate (MTX) or leflunomide or mycophenolate mofetil, hydroxychloroquine (HCQ) or chloroquine (CQ), and NSAIDs, which are all allowed during the study. All background therapy dosages given prior to Screening must have been kept stable according to the specifications in the exclusion criteria for a subject to be eligible for the study. These medications must remain stable during the Screening period and Part A. SOC medications are part of the subject's previous SLE treatment and thus will not be provided by the Sponsor.

Other permitted Medicine

Vitamin D (≥ 400 IU/day) and calcium supplements (≥ 800 mg/day) may be given for prevention of glucocorticoid-induced bone loss (ACR Ad Hoc Committee on Glucocorticoid-Induced Osteoporosis, 2001).

Paracetamol (acetaminophen) may be initiated for pain control of SLE symptoms during the study. This should be titrated off as tolerated, and preferably not taken on the day of the clinic visit. Other pain medications, including opiates, may be used for temporary relief of symptoms not due to SLE.

Vaccines

Subject should be as up to date with childhood vaccinations as much as previous SLE treatments permitted. It is recommended that subjects be vaccinated against infectious diseases according to the local standard of care (i.e. influenza, pneumococcal vaccine, varicella), preferably at least 2 weeks before TD1. It should be noted that live and live-attenuated vaccines are not authorized within 6 weeks before TOFA intake, during the trial period, and for 6 weeks following the last dose of TOFA.

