Cohort 2 subjects will be seen in weekly intervals during Part A.

Cohort 1 and 2 subjects with clinical remission of SLE-CL can enter Part B as early as week 4 post baseline. Subjects who move from Part A to Part B prior to Week 8, will still be evaluated using the same visit schedule as subjects remaining in Part A until week 8.

Part B (week 8* – 24)

The primary objective of Part B is to assess safety and tolerability of TOFA, secondary objectives include effectiveness. Specifically, the PK of TOFA at the 5 mg dose based on Cohort 1 will be characterized.

- If CS are primarily given for SLE-CL, then CS may be decreased for clinically significant improvement as defined by a *Cutaneous Lupus Erythematosus Disease Area and Severity Index (CLASI)* activity score by $\geq 50\%$ from baseline and must be tapered for CLASI activity scores of 0 for > 2 months.

* Roll-over subjects in SLE-CL clinical remission may enter Part B as early as week 4

- If CS are mainly prescribed for other SLE manifestations besides SLE-CL, then CS can be decreased as per the investigator's decision, based on clinically significant findings of improvement.
- If the subject has been discontinued from CS and continues to be in SLE-CL clinical remission (CLASI activity score = 0), then the subject can enter Part C.

Subjects who move from Parts B to Part C prior to Week 24 will still be seen using the same visit schedule as subjects remaining in Part B until week 24.

Part C (week 24[†] – 76)

During Part C all therapies can be altered, per investigator discretion, with the exception of TOFA. The TOFA dose will remain stable throughout the study. Subjects who exit Part A or B early due to SLE-CL improvement will remain in Part C until they have been in the study for a total of 76 weeks.

4. Study description

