8.3 Effectiveness Analyses

Due to the small sample size, results may not show statistical significance. Statistical significance may not be reached in final data analysis. However, a trend towards improved clinical status may assist planning efforts of a larger clinical trial to assess efficacy.

The efficacy population will be all subjects who were enrolled in the study and received at least 1 dose of TOFA. No interim analyses are planned. We will perform intention-to-treat analyses, with the last observation carried forward in primary analyses; and will also perform analyses on observed data in secondary analyses. As this is an open-label study, no control group is available. Efficacy measures are listed under Section 7. Data of subjects who enter Part B before week 8 and/or Part C before week 24 will be

considered on a last-observation (LOC) carried forward basis for endpoints of Part A and B, respectively.

To assess the benefits of TOFA on skin manifestations of SLE, we will use descriptive analysis and contingency table analysis, using Chi-square and Fisher Exact test as appropriate, to determine the proportion of subjects who are partial or complete CLASI responders at weeks 4, 8 and 24 compared to baseline. To assess the effect of TOFA on skin damage, we will compare the change (increase) of CLASI damage score¹⁶ from baseline to the end of Part B and C, respectively, using paired T-tests.

To assess the steroid –sparing properties of TOFA, we will determine the proportion of study subjects who can discontinue steroids at the end of Part B and C, respectively. We will also evaluate steroid sparing properties of TOFA for SLE-CL by comparing steroid doses (absolute and weight-adjusted) at baseline with those in the end of Part B and C, using a paired T-test.

Similarly, we will assess TOFA effect of overall disease activity in SLE as measured by the numeric SLEDAI and BILAG scores, respectively. We will also perform sub-analyses and evaluate improvement or resolution of other organ-system activity (e.g. serological activity – measured by anti-dsDNA antibodies and low complement levels; joint counts) using paired T-tests and contingency table analysis, as appropriate. In a similar fashion the change of the other SLE core response variables (CRV) besides disease activity (SLEDAI, BILAG) will be assessed at each study visit.

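### The steroid-sparing result labelled as being for SLE-CL combines subjects whose steroids are tapered on CLASI with subjects whose steroids are not, and is not split by indication

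*Combined protocol and SAP*

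**What the plan says.** Steroid management depends on why the subject takes CS. Section 3 (Part B) begins one path with "If CS are primarily given for SLE-CL, then CS may be decreased for clinically significant improvement". Section 6.2 repeats it: a taper is allowed at a CLASI activity improvement of at least 50% and required once a score of 0 has been sustained, "provided CS are mainly prescribed for SLE-CL". The second path, in both sections, reads "If CS are mainly prescribed for other SLE manifestations besides SLE-CL, then CS can be decreased as per the investigator's decision". Section 6.2 adds that this applies "even in the setting of complete response of SLE-CL, based on continued improvement of clinical findings of SLE".

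Two further rules move the dose. Section 6.2 allows temporary increases "for new BILAG A or B flares in organ systems other than mucocutaneous organ system". Section 3 (Part C) states: "During Part C all therapies can be altered, per investigator discretion, with the exception of TOFA".

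The exploratory objective for Parts B and C in section 4.3 is "To evaluate steroid sparing properties of TOFA for SLE-CL". Its endpoints are the fall in systemic CS dose (absolute and weight-adjusted) and the share of subjects coming off systemic CS. Section 8.3 says "We will also evaluate steroid sparing properties of TOFA for SLE-CL by comparing steroid doses (absolute and weight-adjusted) at baseline" with the end of Parts B and C, by paired t-test, and also reports the proportion of subjects who stop steroids. The efficacy population is everyone enrolled and dosed. Neither section 8.3 nor Appendix 3, section J (Data Analysis Plan) gives a subset, stratum or covariate for CS indication; section J mentions adjustment for concomitant medications only.

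**The concern.** The protocol treats the indication for CS as decisive when the dose is managed, but the analysis does not use it. In subjects treated mainly for kidneys, joints or another organ, clearing of the skin triggers no taper under the protocol's own rule. Their steroid change therefore says little about whether tofacitinib spares steroids through the skin.

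If such subjects stay on CS for other reasons, a real skin-related effect is diluted. If they taper because other organs improve, a reduction appears under the SLE-CL label that did not come from the skin. Section 8.3 says that trends may help plan a larger efficacy trial, so a mislabelled steroid estimate could be carried into that design. A small sample does not remove this.

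**Working it through.** The plan states no figure for this endpoint: Appendix 3, section D says that no formal sample size estimation was done. There is nothing to reproduce, so the check is a side-by-side reading followed by an illustration.

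**Step 1: rule against endpoint.**

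| Element | CS mainly for skin | CS mainly for other SLE |
|---|---|---|
| Taper before Part C (3, 6.2) | CLASI-based: optional at 50% improvement, required at sustained 0 | Investigator's decision on the course of SLE; no CLASI criterion |
| Increase (6.2) | Non-mucocutaneous BILAG A/B flare | Same |
| Part C (3) | Investigator discretion | Same |
| Endpoints and analysis (4.3, 8.3) | Total systemic CS, all subjects | Same, not separated |

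Pooling is inferred from the absence of any restriction; the plan does not state it in words.

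**Step 2: inputs.** From the documents: 20 subjects, up to 80% on CS (section 3), so at most 0.80 × 20 = 16 CS users. Not in the documents: the share q of CS users treated mainly for other organs, and the stopping rate or dose change in either group. I assume q = 0.25, 0.50 or 0.75. A sizeable other-organ group is plausible: section 3 expects about 50% of subjects on a non-biological DMARD for prior multiorgan involvement, and section 8.2 plans an analysis by history of lupus nephritis.

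**Step 3: formula.** Among CS users, pooled = (1 − q) × skin + q × other. Hence pooled − skin = q × (other − skin). The pooled result equals the skin-indicated result only if q = 0 or both groups change equally.

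**Step 4: proportion stopping CS (hypothetical rates).**

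| q | Skin 50%, other 10% | Skin 30%, other 60% |
|---|---|---|
| 0.25 | 0.75×50 + 0.25×10 = 40% | 0.75×30 + 0.25×60 = 37.5% |
| 0.50 | 30% | 45% |
| 0.75 | 20% | 52.5% |

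The gap from the skin-indicated rate runs from 20 − 50 = −30 to 52.5 − 30 = +22.5 percentage points. These limits come from the assumed inputs and do not estimate the trial's error.

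**Step 5: mean dose change (hypothetical, mg/day).**

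- No change in skin-indicated users and −5 in the others pools to −1.25, −2.5 or −3.75 for q = 0.25, 0.50, 0.75. That would read as sparing for SLE-CL.
- A change of −5 in skin-indicated users and 0 in the others pools to −3.75, −2.5 or −1.25.
- If all 20 subjects enter the test and the four non-users stay off CS, each mean shrinks by 16/20 = 0.8.

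**Step 6: precision after splitting.** Exact (Clopper-Pearson) 95% intervals around an observed 50%:

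| Skin-indicated users | Observed | 95% CI |
|---|---|---|
| 16 (no split) | 8/16 | 25–75% |
| 12 | 6/12 | 21–79% |
| 8 | 4/8 | 16–84% |
| 4 | 2/4 | 7–93% |

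**The case against.** **The label may name the population.** SLE-CL is also the plan's term for the patients studied, so the objective could mean steroid sparing by tofacitinib in those patients, with everyone counted. The endpoints, worded as systemic CS, fit that reading. It does not remove the mismatch: section 6.2 itself sets SLE-CL against other SLE manifestations as reasons for giving CS. It does show that the pooled result is legitimate under a different name.

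**Section 8.3 attaches the label only to the dose comparison.** This is correct. The proportion stopping CS is introduced there as steroid sparing by tofacitinib in general; it falls under the SLE-CL objective only through section 4.3.

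**The contrast between the groups is partial.** A reader might infer that steroids in the second group follow rules unrelated to the skin. The documents do not support this: the decision rests on clinical findings of SLE, which may include skin. What is absent is a CLASI trigger. In the first group, too, a taper at 50% improvement is optional.

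**The skin-indicated subset is not pure.** In Part C every subject's CS are at the investigator's discretion, and temporary increases for non-skin flares apply to both groups. This stands: at week 76 the subset does not isolate skin-driven tapering.

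**Reclassification after seeing CLASI.** A reader might infer that open-label investigators could choose the indication once the CLASI result is known, and so switch the required taper on or off. No section fixes a time for the classification, but this is inference. Medication history is taken at screening, concomitant medications are recorded at every visit, and the CRF is not among the documents, so the indication may already be captured.

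**The endpoint is exploratory, uncontrolled and small.** This is true, and it sets the severity.

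**Conclusion.** The point holds as a mismatch between label and analysis. Tapering is tied to CLASI only in skin-indicated subjects, while the outcome described as sparing for SLE-CL uses total CS in all subjects. The pooled result can be too low or too high as a statement about skin. Neither direction nor size can be determined, because the documents give neither the mix of indications nor the expected changes; the range of −30 to +22.5 points must not be read as an estimate of bias.

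The conclusion rests on two readings: that no restriction by indication is intended, since none is stated, and that SLE-CL in the objective means the skin disease, as in section 6.2. Severity is minor. What is affected is the interpretation of an exploratory endpoint, not a primary or secondary conclusion.

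**What to change.** 1. Add one CRF field at TD1, completed before the first dose: main indication for CS (SLE-CL or other organ). Keep that value fixed for analysis. If the CRF already holds it, cite the field.
2. In section 8.3, report the dose change and the proportion stopping CS among baseline CS users, separately by recorded indication, next to the pooled result.
3. Base any statement about steroid sparing for SLE-CL on the skin-indicated row. Label the pooled row as overall steroid sparing in SLE.
4. State that the end-of-Part-C results reflect investigator discretion in both groups.

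The cost is one field and a few sentences. The skin-indicated row will be small and descriptive, which is why the pooled result should stay beside it and the subset should not become the sole definition of the endpoint. Relabelling alone would be cheaper and lose no subjects, but would leave the objective in section 4.3 unanswered. No change to the steroid rules, visits or sample size is implied.
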